- One participant experiences an SAE deemed possibly, probably or definitely related to study product. This criterion will not be met if it turns out that the participant received NS. SAEs related to malaria or to antimalarial treatment which are expected, will be reported expeditiously but will not fulfill this criterion. If the SAE is unexpected with respect to malaria or antimalarial treatment, it will fulfill the criterion.

If either of these criteria appear to be met by ongoing surveillance at the site, the principal investigator will engage the head of Pharmaceutical Operations on site, or his/her designee, to follow unblinding procedures (see Section 6.6.2 'Unblinding'). To meet the criteria, the participants must actually have received PfSPZ Vaccine and not NS placebo.

After confirmation that a pausing criterion has been met, the Sponsor will contact the SMC to describe the circumstances of the event(s). After an email discussion or, if recommended by the SMC, an ad hoc teleconference, the SMC, which will include the Local Safety Monitor as a voting member, will make a written recommendation about whether or not the study should resume, remain paused pending more data and further review, or placed on full safety hold, and whether or not the affected participants or their caregivers should be unblinded and notified of their treatment assignment. Based on the SMC recommendation, a decision will be made by the Sponsor and principal investigator to either resume the study and continue administration of investigational product in the affected group, to pause the study temporarily in the affected group to allow collection of more data about the triggering event(s) or other safety data, or to institute a full safety hold for the affected group or groups. IRBs (excepting IRBs providing administrative review) and regulatory authorities will be promptly informed of a study pause or of a full safety hold. Their permission will not be required to resume the study but will be required to reverse a safety hold.

Irrespective of the pausing criteria, the Sponsor, LSM, principal investigator or applicable ethical committees or regulatory agencies may decide to pause the study, or to put the study on safety hold based on any constellation of AEs even if the 3 vaccinee threshold is not reached and even if the AEs do not reach Grade 3 severity, or based on any other legitimate reason, such as AEs occurring at another study site or in another study, product quarantine, manufacturing issues, expiry of permissions, out-of-specification stability test results, etc. For a full safety hold to be lifted, there must be written concurrence by the entity or entities that initiated the hold that the study can resume, and this may include regulatory agencies in addition to the IRBs of record.

If a safety hold or study termination is deemed necessary, the applicable ethical committees and regulatory agencies will be notified. For a safety hold to be lifted, there must be written concurrence by the entity or entities that initiated the hold that the study can resume.

7.3 TEMPORARY HOLD OF IMMUNIZATION OR CHMI OF INDIVIDUAL PARTICIPANTS

The administration of PfSPZ Vaccine or PfSPZ Challenge for CHMI to a study participant may be temporarily put on hold for the following reasons:

1. The participant is ill on the day of immunization or CHMI (administration may proceed in the case of a minor illness, based on the investigator's clinical judgment).
2. The participant has an abnormal laboratory value that has been determined to be clinically significant.
3. The participant has taken medication for another acute illness that may affect response to PfSPZ Vaccine or CHMI.
4. The participant has received 3 or more non-live vaccines during the previous 14 days or a live vaccine during the previous 28 days (other than the investigational product) or three or more of any vaccine.
5. At the request of the participant.
6. On the advice of the LSM, IRB, SMC, Sponsor, or FDA.
7. On the advice of the investigators.

Immunization or CHMI will be rescheduled at the earliest possible time within the acceptable window of the originally scheduled immunization or CHMI. Indicated intervals can be shortened or lengthened if circumstances dictate, there is no apparent risk to the participant, and the Sponsor agrees.

7.4 PARTICIPANT DISCONTINUATION/WITHDRAWAL FROM THE STUDY

Participants are free to withdraw from participation in the study at any time upon request. If voluntary withdrawal occurs, the participant will be asked to return for safety follow-up as per determination of the PI. If the participant declines, the end of study form will be completed, and the participant excluded from further study procedures. If a participant withdraws from the study, blood samples previously collected for protocol-specified analyses will be retained. If at the time of consent, a participant gave permission for samples to be collected and retained for non-specified future research they can withdraw this permission at the time of withdrawal from the study and these samples will be destroyed. This withdrawal of consent for future research will be documented. Participants who have received PfSPZ Challenge who withdraw or are withdrawn will receive a complete, appropriate, curative course of antimalarial therapy starting no sooner than the seventh day after PfSPZ Challenge administration. The participant will also be asked to return to the research center for a final safety follow-up on CHMI+28.

The investigator may also permanently discontinue or withdraw a participant from the study procedures for the following reasons:

- The participant starts taking a concomitant medication for a chronic illness that could affect the study outcome variables.
- Pregnancy. The participant will be asked for permission to continue scheduled safety follow-up visits and to complete an end-of-study evaluation as scheduled. The participant will also be asked to allow access to all subsequent health and medical records that pertain to the pregnancy for the duration of the pregnancy and for access to the health and medical records of her infant through one year of age.
- Significant study intervention non-compliance.
- Any clinical adverse event, laboratory abnormality, or other medical condition or situation that occurs such that the site PI considers that continued participation in the study would not be in the best interest of the participant.

- The participant meets an exclusion criterion (either newly developed or not previously recognized) that precludes further study participation.
- The participant is unable to be immunized or undergo CHMI for a period of 30 days or more beyond the date scheduled (plus applicable window) for these procedures.
- Participant is lost to follow-up (see Section 7.5 'Lost to Follow-Up' below).
- On the advice of the LSM, site PI, Sponsor, SMC, IRB, or FDA.

The investigator must promptly notify the Sponsor of this decision and record the reason for participant discontinuation or withdrawal from the study on the CRF and any additional supplemental clinical notes that are required for complete documentation.

7.5 LOST TO FOLLOW-UP

A participant will be considered lost to follow-up if he or she fails to return for three or more scheduled visits and/or is unable to be contacted by the study site staff, as noted below. The following actions must be taken if a participant fails to return to the clinic for a required study visit:

- The site will attempt to contact the participant and reschedule the missed visit within one week, counsel the participant on the importance of maintaining the assigned visit schedule and ascertain if the participant wishes to and/or should continue in the study.
- Before a participant is deemed lost to follow-up, the investigator or designee will make every effort to regain contact with the participant (where possible, via at least 3 emails, texts, telephone calls and/or letters). These contact attempts should be documented in the participant's study file.
- Should the participant continue to be unreachable, he or she will be considered to have withdrawn from the study with a primary reason of "lost to follow-up".
- If loss to follow-up takes place after injection with PfSPZ Challenge, the participant has not been treated for malaria, and attempts to locate the participant have been unsuccessful, the police or other authorities may be requested to aid in the search, due to the potential grave danger posed by untreated malaria.

8. STUDY ASSESSMENTS AND PROCEDURES

8.1 STUDY VISIT SCHEDULE AND FOLLOW-UP PERIODS

The study recruitment, screening, immunizations, administration of PfSPZ Challenge, and follow-up visits will take place at the site clinical center. All participants will actively participate for 15 to 24 weeks (starting from immunization and including CHMI, follow-up visits and final visit but excluding the screening period) depending upon their CHMI cohort. Evaluation of the study vaccine will include collection of solicited and unsolicited AEs, laboratory studies, and physical assessment by clinicians following immunization. The complete schedule of study visits, permitted windows for completing the visits, and evaluations performed at each visit is provided in Section 1.3 'Schedule of Activities'. There will be a specifically defined window for each study visit (allowable days before or after), although participants will be encouraged to be present on the targeted study visit day. The blood volume drawn from each participant will not exceed 5 mL/kg (250 mL for a 50 kg participant) during a 24-hour period and 525 mL per 8-week period (per guidelines of the American Association of Blood Banks). The clinical center may

provide light snacks and refreshments to participants for nutritional support and safety during scheduled and unscheduled study visits, although this is not required if food and drink are readily available from nearby sources.

8.1.1 SCREENING

Screening procedures may occur over multiple visits. The screening visit(s) for participants (immunized and placebo) will be scheduled within 90 days of first immunization. Informed written consent must be obtained from each participant prior to conducting any study procedure. Once consent forms are signed, a unique identification number will be assigned to each study participant. Procedures will be in place to ensure anonymity and de-identification of data. The following activities and procedures will be carried out during the screening visit(s):

- Information about the study will be provided to include a description of clinical trial design, risks, and study schedule. This may be accomplished in person with a member of the study team, or by using IRB approved briefing slides in person or by means of a pre-recorded audio recording.
- Participants will have the opportunity to ask research staff question(s) to assist them in making informed decision about participating in the study.
- Informed consent process will be performed, and the informed consent document (ICD) and other research-related documents will be signed.
- Participants will take a quiz to assess understanding of the study (minimum passing score of 80% required for participation and one repeat testing is allowed if necessary).
- Temperature, pulse rate, blood pressure, height, weight, and BMI will be measured and recorded.
- Inclusion and exclusion criteria will be reviewed.
- Participants will be interviewed to obtain a medical history to include concomitant medications and known allergies.
- Analysis of 5-year cardiovascular risk: This will be performed based upon the method of Gaziano et al (2008) [69]. The risk factors will include sex, age, body mass index (BMI), blood pressure, history of diabetes mellitus, and history of smoking.
- Physical examination will be performed.
- A baseline 12 lead EKG will be performed and results will be reviewed by a cardiologist if deemed necessary.
- Blood samples, as indicated in Section 1.3 'Schedule of Activities', will be collected for:
 - Hematology: (CBC with differential: white blood count, hemoglobin, platelet count, absolute neutrophil count and absolute lymphocyte count);
 - Serum chemistry: glucose, creatinine, alanine aminotransferase (ALT), aspartate aminotransferase (AST);
 - Serology: HBsAg, HCV antibody, HIV-1/2 antigen-antibody 4th generation screen and confirmation (consent will be obtained prior to evaluation of HIV serology);
 - Pregnancy test (serum or urine β -HCG): pregnancy tests will be required of all female participants regardless of age unless reported sterilization, or the participant is menopausal defined as appropriate age with 1 year of amenorrhea. Urine pregnancy tests will be performed on site whereas sera will be sent out for analysis.

All screening laboratories, with the exception of hepatitis and HIV serologies, will be considered expired if performed more than 90 days prior to first immunization. In the event that the screening laboratories

are expired, CBC with differential, glucose, creatinine, ALT, AST and urine/serum pregnancy test will be repeated during the screening follow-up visit and results will be reviewed prior to immunization.

During screening, participants will have blood drawn to determine if any clinical laboratory abnormalities exist that would preclude study participation. In participants who meet all of the inclusion criteria but have an abnormality in one or more screening safety laboratory tests, the site PI may elect to repeat such screening laboratory test(s) to exclude spurious results due to laboratory processing error, etc. The site PI or designee will identify values as abnormal and clinically significant or not clinically significant. Participants that have only mild (Grade 1) abnormalities that are not clinically significant may be included if the study investigator determines that their participation will not present undue risk to the participant. Participants with abnormal labs that are clinically significant will only be enrolled after consultation with the LSM and/or appropriate expert. Participants with one or more clinical laboratory abnormalities greater than mild severity (Grade ≥ 2) will not be enrolled in this clinical trial. If the laboratory abnormality appears related to an intercurrent illness, the site PI can wait until the participant recovers and re-test.

The clinical and laboratory toxicity grading scales that will be used in this trial are based on the Guidance from the Center for Biologics Evaluation and Research, FDA [70] , as well as the site specific laboratory normal reference ranges. Laboratory testing may be repeated if the investigator wishes to confirm specific result(s) that may affect the participant's ability to participate.

Participants who meet all inclusion criteria and none of the exclusion criteria, who have signed the ICD, and have passed the Assessment of Understanding, may be scheduled for immunization and enrollment into the study. Participants excluded from this study because of significant abnormalities will be referred to outside care for evaluation as necessary. In the event of a positive HIV test, the participant will be counseled by a physician investigator and referred for appropriate follow-up care. Notification of state and federal authorities, as required by law, will be the responsibility of the site PI or their designee. For members of the military, notification of command will also be the responsibility of the site PI as required by military regulations.

8.1.2 PRE-IMMUNIZATION VISIT

Participants meeting the entry criteria will return within 7 (± 7) days prior to immunization. The following will occur:

- Study education provided: review of study schedule, contact card (who to contact and how to contact the research site)
- Eligibility criteria will be reviewed
- Vital signs (temperature, blood pressure and pulse)
- Medical history update, physical exam (if indicated), and review of concomitant medications
- The following laboratory tests will be collected:
 - qRT-PCR for malaria (this can be run retrospectively)
 - CBC
 - Immunological Assays: Refer to Section 8.2.3 'Immunology Laboratory Evaluations'.
 - COVID-19 PCR – optional, if clinically indicated

If a participant decides not to continue after completing the Day -7 pre-immunization visit he/she will be a screening failure and will be replaced by an alternate participant on the day of first immunization. The

replacement participant (alternate) will have PCR and immunoassay samples drawn on the day of first immunization (if not completed on Day -7).

The participant may also be withdrawn or decide to withdraw after randomization and prior to first DVI. Up until the time of DVI, this will be considered a screening failure and the individual may be replaced using the same randomization number.

8.1.3 IMMUNIZATION VISITS

The following will occur prior to each immunization:

- Vital signs will be taken (temperature, blood pressure, pulse)
- Medical history, AEs (from V2), SAEs, Concomitant Medication update and targeted physical examination (if indicated) will be performed.
- For women of childbearing potential: results of pregnancy test (urine or blood β -HCG) will be confirmed. Immunization will not proceed unless a negative pregnancy test has been obtained on each day of immunization.
- Eligibility criteria will be reviewed
- Randomization to vaccine and placebo group will occur prior to first immunization only
- The following laboratory tests will be collected (prior to V1 only):
 - Safety: CBC with differential, creatinine and ALT

Participants will be observed for at least 30 minutes following each immunization, have vital signs collected and given memory aids to record local and systemic reactions. After the 30-minute observation period, a post-immunization assessment will be completed before the participants leave including evaluation of vital signs, examination of the injection site, and the recording of solicited and unsolicited AEs. Although breakthrough infections are not expected, participants will be counseled about symptoms and signs of malaria and reminded how to contact study staff if needed at any time.

Alternates

Up to 5 Alternates may be recruited per cohort (not required). Alternates will undergo the pre-immunization visit (see Section 8.1.2 'Pre-Immunization Visit'). These alternates will be asked to be present on the day of first immunization. If an assigned participant does not present on the first day of immunization, elects to withdraw, or is found to have met an exclusion criterion, an alternate will be enrolled into the study, using the same randomization number as the participant who is replaced. An alternate may also replace a participant who withdraws or is withdrawn from the study by the site PI within a 7-day window post- first immunization only. This person will be issued a new randomization number.

Memory Aid

Participants will be provided with a daily memory aid on the day of each immunization. They will be asked to fill out the memory aid once a day for 7 days following each immunization. Participants will be given a thermometer and asked to record temperature, local (x 3d) and systemic symptoms daily. The study staff will review the memory aid with the participant prior to second immunization and 7 days after second and third immunizations. The memory aids will be collected by the study staff but not considered source documents. Failure by the participant to return a memory aid will not constitute a deviation. The memory

aid will be used to help identify solicited AEs during the post-immunization period. These results will be annotated in the participant's study file and/or CRFs.

8.1.4 POST-IMMUNIZATION FOLLOW-UP VISITS

Post-immunization follow-up visits will be scheduled for +2 and +7 days after immunization #2 and , +2, and +14 days after immunization #3. Additionally, other clinical concerns may prompt a study visit based on the judgment of a study clinician.

The following will occur at these visits:

- Vital signs collection (pulse, blood pressure, and temperature)
- Medical history, AEs, SAEs and concomitant medications update
- Targeted physical examination (if indicated)
- Solicited adverse events will be recorded by the study team through +7 days after each immunization
- Unsolicited adverse events will be collected through 21 days post 3rd vaccination for 3 week CHMI participants and through 28 days post 3rd immunization for 12 week CHMI participants.
- Blood collection for safety laboratories and research laboratories as indicated: (see Section 1.3 'Schedule of Activities', Section 8.2.2 'Clinical Laboratory Evaluations' and Section 8.2.3 'Immunology Laboratory Evaluations')
- On each of the days when samples are drawn for "Immune Regulation" studies (see Section 8.2.3.3 'Immune Regulation'), a CBC with differential will be obtained.

There will be a phone call follow-up for all participants on +7 days post immunization 2. The local AEs that will be solicited (Days 0, 1 and 2) are pain, tenderness, erythema, swelling, bruising, pruritus and induration. The systemic AEs that will be solicited are fever (oral temperature ≥ 100.4 F), subjective fever, chills, headache, fatigue/malaise, myalgia, arthralgia, rigors, rash, urticaria, pruritus, edema.

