¹ Screening Visit also includes Assessment of Understanding, Cardiovascular Risk Assessment, height, weight and BMI measurements

² Physicals will be performed during screening. All other physicals will be performed if indicated by medical history

³ Screening serum chemistry: glucose, creatinine, ALT, AST, serum chemistry at all other time points: ALT and creatinine

⁴ Serum β HCG may be substituted

⁵ If a subject is diagnosed with malaria infection, the following samples will be drawn prior to initiation of treatment: CBC w/diff (4mL), Chemistry (5mL), sample for TBS (2mL), sample for UWash PCR (2mL). This will add an additional 13 mL to the cumulative blood volume. qPCR will be performed 28 days post CHMI if subject remains malaria negative. Blood draw for qPCR will be discontinued upon malaria diagnosis and treatment.

12 week CHMI		Screen	Day -7	1	8	10	15	29	31	38	43	113	120	121	122	123	124	125	126	127	128	129	130	131	133	135	138	141	169
Study Day		Day -90 to Day -1	+/- 7	+/- 3	+/- 3	+/- 5	+/- 2	+/- 3	+2	+/- 2	+/- 5	+/- 5	-	-	-	-	-	-	-	-	-	-	-	+/- 2	+/- 2	+/- 7	+/- 10		
Windows		1	2	3	4	5	6	7	8	9	10	11	12	13	14	15	16	17	18	19	20	21	22	23	24	25	26	27	28
Visit Number		Scr ¹	-7	Imm1	Imm2	+2	+7	Imm3	+2	+7	+14	CHMI	+7	+8	+9	+10	+11	+12	+13	+14	+15	+16	+17	+18	+20	+22	+25	+28	+56
Inform ed Consent		X																											
Eligibility Criteria Review		X	X	X	X				X			X																	
Medical History/Update		X	X	X	X	X	X	X	X	X	X	X	X	X	X	X	X	X	X	X	X	X	X	X	X	X	X		
Physical Examination ²		X	X	X	X	X	X	X	X	X	X	X	X	X	X	X	X	X	X	X	X	X	X	X	X	X	X		
Vital Signs (BP, HR, temperature)		X	X	X	X	X	X	X	X	X	X	X	X	X	X	X	X	X	X	X	X	X	X	X	X	X	X		
CBC with differential	EDTA	4	4			4		4	4	4																		4	
Serum chemistry ³	SST	8.5		8.5			8.5			8.5	8.5																	8.5	
HIV ELISA, HbSAg, anti-HCV	SST	3.5																											
COVID-19 PCR (if clinically indicated)		X																											
EKG		X																											
Urine β HCG ⁴		X		X	X			X			X																		
Immunization			X	X				X																					
Provision /Review of Memory Aid			X	X	X	X	X	X	X	X	X	X	X	X	X	X	X	X	X	X	X	X	X	X	X	X			
Telephone Follow Up									X																				
CHMI												X																	
qPCR ⁵		2														2	2	2	2	2	2	2	2	2	2	2	2	2	
Adverse Events / Clinical Events			X	X	X	X	X	X	X	X	X	X	X	X	X	X	X	X	X	X	X	X	X	X	X	X			
SAEs			X	X	X	X	X	X	X	X	X	X	X	X	X	X	X	X	X	X	X	X	X	X	X	X			
Concomitant Medications		X	X	X	X	X	X	X	X	X	X	X	X	X	X	X	X	X	X	X	X	X	X	X	X	X			

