Treatment: The active treatment is three immunizations of 9.0×10^5 PfSPZ of PfSPZ Vaccine administered on days 1 8 and 29 by DVI. The alternative treatment is immunization with normal saline, which is indistinguishable from the test article. Treatment with PfSPZ Vaccine is the only intervention in trial that might affect the near universal susceptibility of US adult residents to Pf infection after administration of the standard dose of 3,200 PfSPZ of PfSPZ Challenge (Pf7G8), which has to date infected 96.4% (27/28) malaria-naïve research participants in four different trials conducted in the US or EU.

Variable of Interest: The primary variable of interest is whether trial participants develop Pf malaria parasitemia following CHMI. This is a dichotomous outcome – infected or not infected, and can be definitively determined during the 28-day follow-up for CHMI because all individuals, except in the rare case of a failed inoculum (currently a 1 in 28 likelihood, or 3.6%), will develop detectable Pf parasitemia if not protected by the vaccine. The risk of failed inoculum will be equivalent in vaccine and placebo recipients, since the study is double-blind and all injections will be done without the possibility of bias based on knowledge of the treatment received. A failed inoculum should occur with equal frequency in

both study groups and therefore should not affect the trial outcome, and the sample size has been calculated anticipating that some controls will not develop parasitemia.

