9. Safety evaluation includes an electrocardiogram (ECG) performed at screening. Participants with abnormal cardiovascular symptoms or findings that appear clinically significant will be excluded and if appropriate, referred to a cardiologist for further evaluation; individuals with history of non-febrile seizures will also be excluded.
10. For the second and third immunizations, allowable windows are assigned (see Section 1.3 'Schedule of Activities').

³ FDA recommendation will be sought.

11. Solicited adverse events will be collected for 7 days after each immunization. The first six days after CHMI, solicited AEs will be assessed for a potential relationship to PfSPZ Challenge; beginning 7 days after CHMI solicited AEs will be assessed for a potential relationship to malaria infection if individuals develop parasitemia. Unsolicited adverse events will be collected from the first immunization (V1) until 21 or 28 days after the third immunization (V3), depending on the timing of CHMI, and for 28 days after CHMI. Physical exams and medical history will be assessed repeatedly as indicated. Safety laboratories will be collected at screening, day of V1, 7 days after V2, 14 days after V3, day of CHMI and 28 days after CHMI.
12. Surveillance for SAEs will occur for the duration of the study.
13. Follow-up of adverse events (including SAEs) and other clinical events will occur until resolution or stability.
14. Participants will be observed for 30 minutes following each dose of PfSPZ Vaccine or PfSPZ Challenge.
15. Clinical laboratory testing will be conducted by certified laboratories.
16. A Local Safety Monitor (LSM) will be assigned to the site, and a Safety Monitoring Committee (SMC) will provide safety oversight.
17. External monitoring will be performed.
18. Electronic case report forms (eCRFs) will serve as the repository of source documents and other relevant data for each study participant. Only information that cannot be collected initially into the CRF (for instance, EKGs and AE medical records) will first be collected onto separate source documents before transcription into the CRF. Laboratory results will be entered from source documents directly into the database.
19. Detection of parasitemia post CHMI will be based upon qPCR. Participants who have 2 positive qPCR results separated by greater than or equal to 12 hours or a single qPCR result reading > 250 estimated parasites/mL will be treated with anti-malaria therapy.

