8.2.1.4 ADVERSE EVENTS (AES) ASSESSMENTS

Solicited AEs:

PfSPZ Vaccine: Surveillance for solicited local AEs will be done for 2 days after each dose of PfSPZ Vaccine. Surveillance for solicited systemic AEs will be done for 7 days after each dose of PfSPZ Vaccine. The list of specific events is detailed in section 8.3.1.1.1 'Solicited Adverse Events'.

PfSPZ Challenge: Surveillance for solicited local AEs will be done for 2 days after the administration of PfSPZ Challenge using the same solicited AE list as is used for PfSPZ Vaccine. Surveillance for solicited systemic AEs will be done for 6 days after PfSPZ Challenge using the same solicited AE list as is used for PfSPZ Vaccine. Surveillance for malaria events will be done from 7 to 28 (CHMI+7 to CHMI +28) days after the administration of PfSPZ Challenge using an expanded list that include the expected signs and symptoms of malaria (See section 8.3.1.2 Malaria Events'). These events are expected as a consequence of Pf parasitemia and will not be considered adverse events.

Unsolicited AEs:

Unsolicited AEs will be collected within 28 days after immunization or CHMI. Collection of solicited and unsolicited AEs will be done before participants leave on the day of immunization and at scheduled visits post immunization. SAEs will be recorded throughout the study.

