8.2.3 IMMUNOLOGY LABORATORY EVALUATIONS

8.2.3.1 ANTIBODY

Time points: pre-immunization, 2 weeks after V2, 2 weeks after V3, CHMI, 28 days post CHMI.

Table 9. Antibody Assays

anti-CSP ELISA (all), IFA and ISI (exploratory); ELISA for other antigens (exploratory), systems serology	Serum 25 mL	3-week CHMI: pre-V1, D15, D43, D50, D78 12-week CHMI: pre-V1, D15, D43, D113, D141
---	----------------	---

Sanaria will conduct its standard ELISA to determine levels of antibodies to Pf circumsporozoite protein (CSP) and may also conduct whole PfSPZ immunofluorescence assay (IFA), inhibition of sporozoite invasion assay (ISI) and ELISA's using other Pf antigens. The laboratory of [name], Professor of Medicine at Harvard Medical School and a Group Leader at the Ragon Institute of MGH, MIT and Harvard, has developed a number of antibody profiling approaches that allow deep interrogation of the role of antibodies in the response to immunization and pathogens. The lab has a particular interest in malaria and malaria vaccines with a goal to understand the role of antibodies in protection against infection following immunization with PfSPZ Vaccine. As a contribution to the USSPZV7 trial, the lab will conduct relevant systems immunology assays including biophysical measurements (isotype, subclass, Fc-receptor binding levels), antibody effector function assays, as well as potential malaria restriction assays in primary human livers.

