A syndromic classification will be used for unsolicited adverse events; e.g., cough, nasal congestion, sore throat will be combined and recorded as “upper respiratory tract infection.” Thus, whenever applicable, the term for the unifying diagnosis will be recorded as the adverse event, not each individual sign or symptom.

Any event not included under the specific list for solicited local or systemic adverse events (see Section 8.3.1.1.1 ‘Solicited Adverse Events’) or malaria events (see Section 8.3.1.2 ‘Malaria Events’ below) will be captured as an unsolicited AE if the AE occurs within 28 days after immunization or CHMI. Events outside of this period will be collected as clinical events.

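### In the 12-week cohort, unsolicited AEs are due through V3+28 (Day 57), but no contact is scheduled from Day 43 to Day 113, so the second half of the window is first asked about 56 to 69 days later

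*Combined protocol and SAP*

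**What the plan says.** Section 3.1 has the vaccine "administered on days 1 8 and 29 by DVI", so V3 is Day 29. Section 4.1, item 11, collects unsolicited events from the first dose "until 21 or 28 days after the third immunization (V3), depending on the timing of CHMI". Section 8.1.4 gives 21 days for the 3-week cohort and, for the other cohort, "through 28 days post 3rd immunization for 12 week CHMI participants".

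The clinic visits that section 8.1.4 lists after V3 are "2, and +14 days after immunization #3". In Table 3 (section 1.3) the 12-week schedule around V3 runs "29 31 38 43 113 120". The antibody sampling days in section 8.2.3.1 agree: "12-week CHMI: pre-V1, D15, D43, D113, D141".

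Section 8.2.1.4 says that collection of solicited and unsolicited events "will be done before participants leave on the day of immunization and at scheduled visits post immunization". The memory aid in section 8.1.3 covers the 7 days after each dose. The next scheduled update of adverse events, serious events and medications is the one done before challenge (section 8.1.5).

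Section 8.3.1.1.1.1 states a single rule for all participants: an event outside the solicited and malaria lists "will be captured as an unsolicited AE if the AE occurs within 28 days after immunization or CHMI". Sections 8.2.1.4 and 8.3.4 give the same 28 days.

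**The concern.** The protocol sets a 28-day observation window in the 12-week cohort, but its schedule enquires promptly about only the first half. Related unsolicited events belong to a primary safety endpoint (synopsis and section 3.2). Each event needs an onset date and time, duration, severity and relationship (section 8.3.5), and severity rests on how far the event interfered with routine activities (section 8.3.3.1). These are hard to reconstruct after two months.

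Timing also matters for serious events. Under section 7.2, one related serious event in a vaccinee meets a pausing criterion. The safety committee's two scheduled meetings fall before the start of the trial and after the final safety report (section 10.1.8), so review during the trial depends on the site learning of the event.

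Separately, the 3-week cohort's V3 window ends at either 21 or 28 days depending on the section. Under the longer version it runs into the first week after challenge.

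**Working it through.** This is day arithmetic; no power or sample-size formula applies.

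**Inputs**
- V3 on Day 29 (section 3.1).
- V3 window of 28 days in the 12-week cohort and 21 days in the 3-week cohort (sections 4.1 and 8.1.4).
- Contacts on Days 29, 31, 38, 43, then 113 in the 12-week cohort; Day 43, then Day 50 in the 3-week cohort (Table 3).
- 22 or 23 vaccinees and 7 or 8 controls challenged at 3 weeks, the rest at 12 weeks (section 4.2).
- Telephone compensation of $15 per call (Table 14).

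**The plan's own days reproduce**
- V3 + 14 = 29 + 14 = Day 43.
- V3 + 3 weeks = 29 + 21 = Day 50.
- V3 + 12 weeks = 29 + 84 = Day 113.

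**12-week cohort**
- Window end: 29 + 28 = Day 57.
- Days after the last prompt visit: 44 to 57, so 57 − 43 = 14 days, and 14/28 = 50%.
- Delay to the next scheduled enquiry: 113 − 57 = 56 days for the latest events and 113 − 44 = 69 days for the earliest.
- Participants affected: 22 + 7 = 29 to 23 + 8 = 31, about 30 of 60.

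**3-week cohort**
- The 21-day window closes on Day 50, the challenge day, and 50 − 43 = 7 days.
- There is no comparable gap.

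**Does any other scheduled contact fall in the gap?**
- The memory aid for V3 ends 7 days after the dose.
- Table 3 has one telephone contact, but no column lies between Day 43 and Day 113, so the call cannot fall in the gap wherever its mark belongs.

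**Sensitivity to visit windows** (the windows row is misaligned in the text available, so shifts of up to 5 days are assumed)
- Day 43 visit on Day 38: 57 − 38 = 19 days uncovered (68%). On Day 48: 57 − 48 = 9 days (32%).
- Challenge on Day 108: delay at least 108 − 57 = 51 days. On Day 118: at most 118 − 44 = 74 days.

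**Scale**
- Counted from V1 (Days 1 to 57), the uncovered part is 14/57 = 25%.
- Assuming 30 participants per cohort, it is 30 × 14 = 420 of 30 × 28 + 30 × 21 = 1,470 post-V3 person-days, or 29%.

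**With one contact on Day 57**
- Longest delay for Days 44 to 57: 57 − 44 = 13 days.

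**The case against.** The strongest reply is that the protocol does not rely on scheduled contacts alone. Participants have round-the-clock access to the team (section 8.2.1.5), may ask for unscheduled visits at which adverse events are documented (section 8.1.7), and a clinical concern may prompt a visit (section 8.1.4). This stands. A reader might infer that the second half of the window is captured only by recall, but that is true of scheduled enquiry alone. The unscheduled routes depend on the participant coming forward or on a concern already known.

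A reader might also infer that pooling the two cohorts biases the vaccine-placebo comparison. The documents do not support this: treatment is blinded and randomization is blocked to keep about 3:1 within each challenge cohort (section 6.6.1). Ascertainment differs by cohort, not by arm.

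Nor do the documents show that antimalarial-active drugs taken in the gap would pass unnoticed into challenge. New medications must be discussed with the team (section 6.8), medications are updated before challenge (section 8.1.5), and section 7.3 lists medication that may affect the challenge as a reason for a hold.

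The effect on the endpoint is not quantified. The reactions described in section 2.2.1.1.2 came within about a day of dosing, the synopsis limits the endpoint to moderate, severe or serious related events, and section 9.1.1 says the sample size was not designed for a formal safety hypothesis. These points limit the importance of the gap. They do not remove it, because the protocol itself specifies 28 days, and the endpoint as worded in section 3.2 has no severity limit.

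Finally, the 21-day versus 28-day conflict loses no data. In the 3-week cohort a new 28-day collection period opens at challenge. Only the window to which an event is attributed is unclear.

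**Conclusion.** The gap is real and follows from the protocol's own days. Carried out as written, the plan first asks about 14 of the 28 post-V3 days after 56 to 69 days in about 30 of 60 participants, against at most 7 days in the 3-week cohort. This assumes visits on their nominal days; with shifts of up to 5 days the uncovered share is 32% to 68% and the delay 51 to 74 days.

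The likely consequence is loss of completeness and of precision in dating and grading, in both arms. A serious event in Days 44 to 57 that is not self-reported could be learned of up to 69 days late; the 70 days between visits is the spacing of contacts, not the longest delay. How many events would be missed cannot be estimated from the documents, and no biased treatment comparison has been shown. The change is worthwhile because it is cheap; the trial's conclusions do not hinge on it.

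**What to change.** - **Add one scripted telephone contact at V3+28 (Day 57)** for 12-week participants, in Table 3 and section 8.1.4, covering unsolicited events, serious events and concomitant medications.
- **Reconcile the 3-week cohort's V3 window.** It is 21 days in sections 4.1 and 8.1.4, and 28 days in sections 8.2.1.4, 8.3.1.1.1.1 and 8.3.4. Events after challenge should be attributed to one defined window.

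**Cost:** staff time for about 30 calls, about 30 × $15 = $450 in participant compensation (29 to 31 calls: $435 to $465), and a protocol amendment with the consent revision that section 10.1.2.2 requires. No blood draw or clinic visit is added.

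**What it leaves:** the cohorts are still not ascertained identically (up to 13 days' delay against at most 7). A serious event after the call would still first be asked about at challenge: for Day 58, 113 − 58 = 55 days later. Restricting the pooled safety comparison to a common window ending at V3+21 is an analyst's preference, not something this finding requires.
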